7.2.3 PER-PROTOCOL POPULATION

The PP population will include subjects who complete the Week 12 evaluation without noteworthy study protocol violations (i.e., any subject or investigator activity that could have possibly interfered with the therapeutic administration of the treatment or the precise evaluation of treatment efficacy). The PP population will include subjects in the safety population who do not meet any of the following criteria:

- Violated the inclusion/exclusion criteria;
- Have taken any interfering concomitant medications;
- Did not attend the Week 12 visit, with the exception of a discontinuation from the study due to an adverse event related to study treatment or documented lack of treatment effect;
- Have missed more than one interim study visit;
- Have not been compliant with the dosing regimen (i.e. subjects must apply 80-120% of the expected applications of study medication during participation in the study);

- Out of visit window at the Week 12 visit by ± 5 days;

Prior to breaking the blind, other additional criteria may be added to the list to accommodate for unforeseen events that occurred during the conduct of the trial that result in noteworthy study protocol violations.

7.3 DEMOGRAPHIC AND BASELINE CHARACTERISTICS

Subject demographic and baseline characteristics will be summarized by treatment group for the ITT, PP and safety populations. For continuous variables (e.g. age), mean, median, standard deviation, minimum and maximum will be presented. Categorical variables (e.g., ethnicity, race) will be summarized with frequency count and percentage by treatment group.

7.4 DESCRIPTIVE STATISTICS

Descriptive statistics will be presented for the efficacy data at each evaluation for the ITT and PP populations. Safety data will be summarized as indicated below for the safety population.

Continuous data will be summarized with sample size (N), mean, median, standard deviation, minimum and maximum. Categorical data will be summarized with N, frequency counts, and percentages.

Descriptive statistics will be presented for the active treatment groups, each vehicle treatment group, and the vehicle treatment groups combined.

7.5 EFFICACY ANALYSIS

Lesion counts will be summarized at each evaluation from Baseline through Week 12. Absolute and percent change in lesion counts will be summarized at Weeks 2, 4, 8, and 12. IGA scores will be summarized from Baseline through Week 12. The dichotomized IGA scores will be summarized at Weeks 2, 4, 8, and 12.

Primary Efficacy Analysis

The analysis of the absolute change in non-inflammatory lesion counts at Week 12 will be conducted using an analysis of covariance with factor of treatment and baseline lesion count as the covariate.

The analysis of the absolute change in inflammatory lesion counts at Week 12 will use the same method as the analysis of the non-inflammatory lesions.

The analysis of the dichotomized IGA scores at Week 12 will be analyzed with a Cochran-Mantel-Haenszel test.

Pairwise comparisons of each active treatment group to the combined vehicle treatment group will be computed without concern for controlling for multiplicity.

Secondary Efficacy Analyses

The analyses of percent change in inflammatory and non-inflammatory lesion counts at Week 12 will use the same method as the analysis of the non-inflammatory lesions.

The time to improvement will be compared between each of the active treatment groups and the combined Vehicle treatment group using the Kaplan-Meier method. An observation will be censored if improvement is not achieved by Week 12 (inclusive). The log-rank test will be used to compare time to response between each active treatment group and the combined Vehicle treatment group.

7.5.1 SENSITIVITY EFFICACY ANALYSES

A sensitivity analysis will use the method of Markov Chain Monte Carlo (MCMC) multiple imputation to impute missing data for the non-inflammatory and inflammatory lesion counts and IGA at Week 12. This method does not rely on the assumption of data missing at random. Additionally, the pattern of missing observations in each treatment group cannot influence the missing value estimation in the other because the imputation is being conducted independently for each treatment group.

Lesion Counts

Multiple imputation and subsequent analysis will involve four distinct phases with these principal tasks:

1. Calculate the number of missing values to be estimated by MCMC (nmiss) for 12 week value.
2. Create a data set of subjects, one for each treatment group, with observed values and those needing estimation by MCMC. The missing lesion count values in each data set will be filled in using the MCMC method ‘5 x nmiss’ times to generate ‘5 x nmiss’ data sets. The resulting data sets for each treatment group will be combined into one complete data set for each imputation.

Syntax:

```
proc mi data=datain out=dataout seed=&seed. nimpute=5xnmiss;
  where trtpn=(1, 2,, 3, 4, or 5);
  mcmc chain=multiple;
  var lescnt2-lescnt5;
run;
```

3. For each complete data set, the absolute change in non-inflammatory lesion counts and absolute change in inflammatory lesion counts for baseline minus the 12 week value will be computed. Each complete data set will be analyzed as specified for the particular analysis.

The results from these analyses will be combined into a single inference using SAS PROC MIANALYZE.

IGA

The sensitivity analysis for the IGA multiple imputation will involve four principal tasks:

1. Calculate the number of missing values, by treatment group, for IGA (total from Weeks 2, 4, 8, and 12).
2. Missing values will be filled in '5 x nmiss' times to generate '5 x nmiss' complete data sets, where nmiss is the maximum number of missing values of both treatment groups. The resulting imputed datasets for each treatment group will be combined into one complete dataset by imputation number.

Syntax:

```
proc mi data=datain out=dataout seed=&seed. n impute=5 x nmiss;
  where trtpn=(1, 2, 3, 4, or 5);
  mcmc chain=multiple;
  var IGA1 IGA2 IGA4 IGA8 IGA12;
run;
```

3. For each complete dataset, dichotomous endpoints (defined as IGA = 0 or 1 and at least a two-grade reduction from Baseline) will be computed. The imputed IGA values will be rounded to the nearest integer value prior to computing the dichotomized endpoints. Each complete data set will be analyzed with a Cochran-Mantel-Haenszel test.

Results from these analyses will be combined into a single inference using SAS® PROC MIANALYZE.

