Study visits should occur at approximately the same time of day throughout the study.

PROCEDURES	Screening (Day -35 to Day -1)	Baseline (Day 0)	Week 2 ¹ ±3 days (Day 14)	Week 4 ±3 days (Day 28)	Week 8 ±5 days (Day 56)	Week 12/ET ² ±5 days (Day 84)
Informed Consent/Assent	X					
Demographics	X					
Medical History	X	X				
Medication History	X	X				
Inclusion/Exclusion Criteria	X	X				
Brief Physical Examination	X	X ³				X
Chemistry, Hematology, PT/PTT	X	X ³				X
Urine Pregnancy Test (all WOCBP)	X	X ³		X	X	X
Methemoglobin	X	X	X			X
Blood Pressure and Pulse	X	X	X	X	X	X
IGA	X	X	X	X	X	X
Lesion Counts	X	X	X	X	X	X
Cutaneous Tolerability Evaluation		X	X	X	X	X
Instruct on Study Drug Application and Provide Subject Instructions		X				
Study Drug and Diary Dispensed		X	X	X	X	
Study Drug and Diary Collected			X	X	X	X
Subject Compliance Reviewed			X	X	X	X
Photography		X				X
Concomitant Medications	X	X	X	X	X	X
Adverse Events	X	X	X	X	X	X

¹ All visit dates are in reference to Baseline, e.g., Visit 2 occurs two weeks (14 days) after Baseline visit

² All Week 12 procedures should be completed for subjects who prematurely discontinue.

³ If the Baseline Visit is within 3 calendar days of the Screening visit, Physical Examination, Chemistry, Hematology, PT/PTT, and UPT do not need to be repeated.

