- When a subject is lost to follow-up. The Investigator will try twice to reach the subject by telephone and will send a certified follow-up letter before considering that the subject is lost-to-follow-up. These actions will be reported on the subject's study record and a copy of the follow-up letter maintained in the Investigator's file.

Refer to Section 6.7 for a discussion of criteria for discontinuation of individual subjects from the study.

All premature discontinuations and their causes must be carefully documented by the Investigator on the subject's study record and in the study database. In no case will a subject who has been assigned a study number and randomized into the study be replaced by another.

All Week 12/ET evaluations should be performed at the time of premature discontinuation. All data gathered on the subject prior to termination will be made available to QST and Novan.

Study completion or reason(s) for discontinuation as listed in the study record will be entered into the study database as follows:

- Completed
- Adverse Event
- Lack of Efficacy
- Withdrawal by Subject
- Physician Decision
- Protocol Violation
- Lost to Follow-Up
- Pregnancy
- Worsening of condition

- Other

Novan has the right to terminate or stop the study at any time. Should this be necessary, both QST and the Investigator will ensure that proper study discontinuation procedures are completed.

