7. STATISTICAL ANALYSIS

7.1 GENERAL CONSIDERATIONS

All statistical processing will be performed using SAS® version 9.3 unless otherwise stated. Statistical significance will be based on two-tailed tests of the null hypothesis resulting in p-values of ≤ 0.05 unless stated otherwise. Inferential testing will compare each active treatment group to the combined Vehicle treatment group. Comparisons will not be performed between active treatments. Efficacy analyses will be performed for the intent-to-treat (ITT) and per-protocol (PP) populations. Safety analyses will be performed using the safety population.

For the dichotomized IGA, subjects will be considered a success if their IGA score is clear or almost clear and at least two grades less than Baseline.

For those subjects for whom no Week 12 assessments are available, the last observation will be carried forward (LOCF) in order to provide a value for efficacy parameters that are missing, primarily due to missed visits. Additionally, a sensitivity analysis to estimate missing efficacy data will be based on estimation using the method of Markov Chain Monte Carlo (MCMC) independently for each treatment group. All hypotheses will be two-sided at an alpha level of 0.05.

A detailed description of the statistical methodology and data reporting for this study will be provided in the Statistical Analysis Plan (SAP). The SAP will be finalized before the database is locked and released to Novan. Any deviations from the SAP will be justified in the clinical study report.

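### Section 7.5.1 says the MCMC imputation is free of the missing-at-random assumption, but the PROC MI code printed there assumes it within each arm

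*Protocol*

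**What the plan says.** Section 7.1 makes LOCF the rule for subjects without a Week 12 assessment, "in order to provide a value for efficacy parameters that are missing, primarily due to missed visits". It adds one sensitivity analysis, MCMC multiple imputation done separately by arm.

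Section 7.5.1 describes that analysis and states: "This method does not rely on the assumption of data missing at random". As a further property, it says one arm's missing-data pattern cannot affect another arm's imputed values, because "the imputation is being conducted independently for each treatment group".

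The code follows. For lesion counts it is PROC MI restricted to one treatment group, with "mcmc chain=multiple" and "var lescnt2-lescnt5". For IGA it is the same call with five IGA scores in the variable list, followed by this step: "The imputed IGA values will be rounded to the nearest integer value prior to computing the dichotomized endpoints". Results are pooled with PROC MIANALYZE.

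On early withdrawal, footnote 2 of Table 2 (Section 4.1) says: "All Week 12 procedures should be completed for subjects who prematurely discontinue". Section 4.1.7 repeats the request: "All Week 12/ET evaluations should be performed at the time of premature discontinuation".

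**The concern.** The sentence gives the method a property it lacks. PROC MI with an MCMC statement and nothing else fills in missing values from a multivariate normal model fitted to the observed values. Such imputations are valid if, given the variables in the model, the chance of being missing does not depend on the unseen value. That is the MAR assumption.

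What is at stake is interpretation. The protocol foresees losses that may relate to outcome: withdrawal for lack of efficacy and a recorded reason of worsening (Section 4.1.7), and discontinuation for severe intolerance (Section 6.7). A reader relying on Section 7.5.1 could take agreement between LOCF and MCMC as evidence that such losses do no harm. An analysis that itself assumes MAR cannot show that.

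**Working it through.** **1. Reading the code against the sentence.** Each PROC MI call holds three things: a restriction to one arm, the MCMC statement, and a list of visit values. Sections 7.1 and 7.5.1 contain no MNAR statement, delta shift, reference-based imputation, dropout-pattern indicator or reason for withdrawal. Nothing therefore lets an unseen value differ systematically from what the arm's observed data predict. The separate runs mean only that the conditioning set is arm plus the listed values. The protocol's second statement, that arms do not influence each other, is true but is a different property.

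**2. Does the method behave as if it relied on MAR?** The protocol states no figure to reproduce, so every input here except arm size is assumed. Section 7.8 gives about 50 per active arm and 25 per vehicle arm, hence 25 + 25 = 50 in the combined vehicle group.

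*Single arm.* n = 50, four visits, SD 10, lag-1 correlation 0.6, about 20% missing at Week 12, 300 replicates, data-augmentation MCMC under a normal model:

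| Week 12 missingness depends on | Bias of imputed mean (simulation SE) | Complete-case bias |
|---|---|---|
| observed Week 8 count (MAR) | -0.1 (0.10) | -1.3 |
| unseen Week 12 count (not MAR) | -1.3 (0.08) | -2.0 |

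*Two arms.* 200,000 per arm, SD 12, correlation 0.75^lag, true difference -5.01 lesions. Dropouts miss Weeks 8 and 12. Week 12 is imputed by arm from a normal model on Weeks 2 and 4, followed by ANCOVA. Negative bias favours active.

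| Mechanism | Dropout, active/vehicle | Bias |
|---|---|---|
| MAR | 10/10, 20/20, 20/10, 30/10% | -0.01, -0.02, 0.00, -0.02 |
| Not MAR | 10/10, 20/20% | 0.00, -0.01 |
| Not MAR | 20/10, 30/10% | -0.73, -1.41 |
| Not MAR, 50% of dropouts with an early-termination (ET) value used as Week 12 | 20/10, 30/10% | -0.30, -0.50 |
| Not MAR, 80% with such a value | 20/10, 30/10% | -0.10, -0.18 |

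Unequal dropout does no harm while MAR holds. The difference is biased when MAR fails and dropout also differs between arms.

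**3. Size by formula.** Let d be the departure from MAR in lesions, m the fraction imputed (A active, V vehicle) and e the share of dropouts whose ET value serves as Week 12. The protocol does not state that mapping.

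- m = dropout × (1 - e); bias = d × (mA - mV), taking d as equal in both arms.
- d = 5, e = 0: 5 × (0.20 - 0.10) = 0.50; 5 × (0.30 - 0.10) = 1.00.
- d = 5, e = 50%: 0.25 to 0.50. At e = 80%: 0.10 to 0.20.
- d = 2: 0.20 to 0.40, 0.10 to 0.20 and 0.04 to 0.08 at the same three values of e.
- SE = SD × sqrt(1/50 + 1/50) = 0.2 × SD, which is 2.0 at SD 10 and 3.0 at SD 15.
- d = 5 in SE units at e = 0: 0.50/3.0 = 0.17 to 1.00/2.0 = 0.50. At e = 50%: 0.08 to 0.25. At e = 80%: 0.03 to 0.10.

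The formula is rough. The two-arm simulation corresponds to d of 0.73/0.10 = 7.3 and 1.41/0.20 = 7.1 at e = 0, so it is a stronger departure than d = 5.

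**The case against.** The best case on the other side concerns weight, not correctness.

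- **One sentence about a supporting analysis.** LOCF is the main rule, comparisons are made without multiplicity control (Section 7.5), and Section 7.8 claims no power. The harm lies in how results might later be worded. This stands as a limit on importance, but it does not make the sentence true.
- **Direction.** The scenarios above put more dropout on active, and the protocol gives no ground for that; Section 1.4 reports similar adverse event profiles. This stands. With 10/20 and 10/30% dropout, a rerun gives +0.74 and +1.48 lesions, against active. The direction in this trial is unknown.
- **Near a worst case.** The two-arm simulation removes Week 8 as well as Week 12. Keeping Week 8 reduces the bias at e = 0 to -0.48 and -0.96. Withdrawal for lack of efficacy may be judged on observed scores, which is compatible with MAR, and ET visits are requested. These points stand and reduce the likely size.
- **The SAP.** Section 7.1 leaves detailed methodology to the SAP, which I have not seen. It may contain a not-at-random analysis. That bears on whether to add one, not on the error in this document.

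**Conclusion.** The concern holds. The method in Section 7.5.1 assumes MAR within treatment group, given the variables in the imputation model, together with multivariate normality; the protocol says otherwise. That conclusion comes from the code and depends on no assumed number.

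The practical effect is limited. No primary result changes, and with equal dropout and equal departure in both arms the treatment difference is almost unbiased. Under the assumed imbalances the bias is a fraction of a standard error, in either direction, and it shrinks as more early leavers have an ET assessment that counts as Week 12. The sentence should be corrected because it invites a claim of robustness that the analysis cannot support.

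**What to change.** Replace the sentence with: *This method assumes data are missing at random within treatment group, given the variables in the imputation model, and multivariate normality.* That alone cures the error.

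If the SAP already has a not-at-random analysis, cross-refer to it. Only if it does not, add a delta-adjusted tipping point on the imputed data sets:

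- **Lesion counts:** raise imputed active-arm Week 12 counts in steps of 1 lesion and rerun the ANCOVA and PROC MIANALYZE. For any comparison significant at shift 0, report the shift at which significance is lost. Each step moves the estimate by mA lesions.
- **IGA:** a lesion-unit shift does not apply. Either shift the imputed score by quarter grades before rounding, or count imputed subjects as non-successes. With an assumed imputed mean of 2.2 and SD of 0.9, and success meaning a score below 1.5, success among imputed subjects is 21.8, 14.6, 9.1, 5.4 and 2.9% at shifts of 0, 0.25, 0.5, 0.75 and 1.0. Quarter steps are therefore graded, while a whole grade is already close to counting all as failures.

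The cost is one corrected sentence and, if needed, a short program on data sets that will already exist. It needs no extra patients or visits. The added analysis may make the sensitivity result look less favourable.

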3.7.2 INCLUSION CRITERIA

Each subject must fulfill all of the following inclusion criteria to participate in the study:

1. Have a signed written informed consent form (ICF). Subjects less than 18 years of age or the age of majority in their state must sign an assent form for the study and a parent or a legal guardian must sign the informed consent;
2. Be male or female, 12 to 40 years of age, inclusive and in good general health;
3. Have a baseline IGA score of moderate (3) or severe (4);
4. Have a minimum of 25 but not more than 70 non-inflammatory lesions (open and closed comedones) on the face;
5. Have a minimum of 20 but no more than 40 inflammatory lesions (papules and pustules) on the face;
6. Have no more than two nodules or cysts on the face;
7. Women of childbearing potential (WOCBP) must have a negative urine pregnancy test (UPT) prior to randomization;
8. WOCBP must agree to use an effective method of birth control during the course of the study and for 30 days after their final study visit; females taking hormonal contraceptives must have taken the same type for at least three months (90 days) prior to entering the study and must not change type during the study. Those who have used hormonal contraceptives in the past and stopped must have discontinued usage at least three months prior to the start of the study;
9. Males must agree to avoid fathering a child during the study and for 60 days after the last dose of the study drug by ensuring one of the acceptable methods of contraception listed is used and not donating sperm; and
10. Be willing and able to follow study instructions and likely to complete all study requirements. Subjects under 18 years of age or age of majority must be accompanied by the parent or legal guardian at the time of assent/consent signing.

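### The lesion-count imputation code names four variables for five time points, so it omits either the baseline count the ANCOVA adjusts for or the Week 12 endpoint

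*Protocol*

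**What the plan says.** Section 7.5.1 gives SAS code for the sensitivity analysis of missing lesion counts. It is run separately for each treatment group, with the variable list "var lescnt2-lescnt5". The variable names are not defined. After imputation, step 3 says the "absolute change in inflammatory lesion counts for baseline minus the 12 week value will be computed", and likewise for non-inflammatory counts. Each completed data set is then analysed as in Section 7.5, by "analysis of covariance with factor of treatment and baseline lesion count as the covariate".

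For IGA, the same section uses "var IGA1 IGA2 IGA4 IGA8 IGA12", which is five variables.

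Table 2 (Section 4.1) schedules lesion counts at Screening, Baseline and Weeks 2, 4, 8 and 12. Its first footnote gives as an example that "Visit 2 occurs two weeks (14 days) after Baseline visit". Its second footnote adds: "All Week 12 procedures should be completed for subjects who prematurely discontinue".

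The main handling of missing data is in Section 7.1: "the last observation will be carried forward (LOCF) in order to provide a value for efficacy parameters that are missing".

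**The concern.** A numbered list of four cannot cover Baseline and four post-baseline visits. On the likelier reading Baseline is left out, so imputation ignores a variable that both defines the endpoint and serves as the ANCOVA covariate. The two models are then uncongenial.

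The subjects most exposed are those with no post-baseline count. Section 7.2.1 keeps them in the ITT population because it requires only randomization and dispensing. None of their own data enter the model, so their Week 12 value is drawn from their arm's general distribution whatever their baseline severity. Subjects with a Week 2, 4 or 8 count bring in baseline information indirectly.

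Because imputation is by arm, baseline-related dropout that differs between arms passes into the treatment contrast. If more severe subjects leave the active arm, their imputed counts are too low and the benefit is overstated. That is an unwelcome direction for the only alternative to LOCF that the protocol specifies for two of its three co-primary endpoints.

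**Working it through.** **1. Counting.** The listed variables are `lescnt2`, `lescnt3`, `lescnt4` and `lescnt5`: 4. The time points from Baseline are Baseline and Weeks 2, 4, 8 and 12: 5.

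| Numbering | 2 | 3 | 4 | 5 | Left out |
|---|---|---|---|---|---|
| Visit 2 = Week 2 (Table 2 footnote) | Week 2 | Week 4 | Week 8 | Week 12 | Baseline |
| Screening = 1 | Baseline | Week 2 | Week 4 | Week 8 | Week 12 |

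The second reading cannot be intended, since Week 12 is the value to be imputed. No consecutive numbering covers both ends. In the IGA list the suffixes 2, 4, 8 and 12 are the weeks, so `IGA1` can only be the pre-treatment score.

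**2. Inputs for the size.** From the protocol: "Have a minimum of 20 but no more than 40 inflammatory lesions (papules and pustules) on the face" (Section 3.7.2), and arms of about 50, with 25 + 25 on vehicle (Section 7.8). Assumed, because the protocol does not give them:
- true effect −5 lesions (negative favours active) and Week 12 SD 12;
- baseline uniform over 20 to 40, so SD = 20/√12 = 5.8;
- baseline to post-baseline correlation r = 0.3, 0.5 or 0.7;
- 15–20% dropout, with baseline-dependent dropouts 5 lesions worse at baseline than completers.

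**3. Hand check of the extreme case.** Suppose all dropout is before Week 2 and depends on baseline in the active arm only. Dropouts are imputed around the completers' mean, so

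error in the contrast = dropout rate × slope of Week 12 on baseline × baseline gap, with slope = r × 12/5.77.

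The slopes are 0.62, 1.04 and 1.46. At 20% dropout the error is 0.20 × 5 × slope = 0.62, 1.04 and 1.46. Simulation gives 0.61, 1.05 and 1.45.

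**4. Large-sample simulation.** 400,000 per arm, monotone dropout, normal-model imputation by arm, then ANCOVA of change on arm and baseline. The first missing visit falls 25/25/25/25% (even) or 40/30/20/10% (mostly early) over Weeks 2/4/8/12. The last column gives the bias without baseline, in lesions, at the three correlations. Rounding can make it differ by 0.01 from the other columns.

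| Dropout depends on baseline in | Estimates at r = 0.5: full data / without baseline / with baseline | Bias at r = 0.3 / 0.5 / 0.7 |
|---|---|---|
| Both arms equally, mostly early | −5.03 / −5.03 / −5.03 | at most 0.03 |
| Active only, all after Week 8 | −5.02 / −5.19 / −5.01 | 0.14 / 0.18 / 0.17 |
| Active only, even | −4.99 / −5.46 / −4.99 | 0.33 / 0.47 / 0.54 |
| Active only, mostly early | −5.00 / −5.60 / −4.99 | 0.41 / 0.60 / 0.72 |
| Same, 70% give a usable early-termination count | −5.00 / −5.39 / −5.00 | 0.30 / 0.40 / 0.41 |
| Active only, all before Week 2 (extreme) | −5.04 / −6.08 / −5.05 | 0.61 / 1.05 / 1.45 |
| Opposite directions, even (extreme) | −4.99 / −5.92 / −4.99 | 0.61 / 0.93 / 1.07 |

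Dropout that is random gives at most 0.03, and dropout that depends on the observed Week 2 count gives at most 0.02. If dropouts are only 2.8 lesions worse at baseline, the active-only even case falls to 0.18 / 0.26 / 0.28. With baseline in the model, bias is at most 0.03 in every scenario.

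For non-inflammatory counts (25 to 70 entry range, Week 12 SD 18, r = 0.5 to 0.7), the active-only even case gives 0.69 to 0.80 lesion.

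**5. Trial size.** 1000 simulated trials of 50 v 25 + 25, imputed separately, 25 imputations each, active-only dependence, mostly early, r = 0.5. The mean estimate is −5.67 without baseline and −5.03 with it (Monte Carlo SE 0.08). The gap is 5.67 − 5.03 = 0.64, and 0.64/2.5 ≈ 0.25 of the pooled SE. Coverage of the 95% interval is 95.3% either way.

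**6. Other assumptions.** A separate simulation (60,000 per arm) used effect 3, slopes 0.5 to 0.8, residual SD 8, dropout 10–30%, and 30–100% of dropouts before Week 2. The inflammatory shift between the two imputation models was at most 0.02 when dropout was unrelated to baseline or equally related in both arms. It was 0.11 to 1.26 for active-only dependence.

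**The case against.** The best counter-argument accepts the count of four against five and disputes how much it matters.

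- *Only a sensitivity analysis is touched.* The main analysis uses LOCF, the trial is Phase 2 with no stated power target, and no decision rule depends on this estimate. This stands.
- *The harm is conditional and small.* The bias needs dropout that depends on baseline itself, differs between arms, and occurs before much post-baseline data accrue. Nothing in the protocol suggests that pattern. Coverage did not change. This stands as a limit on size.
- *The assumed slope is high.* A Week 12 SD of 12 at r = 0.5 implies a slope of 1.04. With slopes 0.5 to 0.8, residual SD 8 and 17% dropout, the active-only shift is 0.18 to 0.25 lesion (even) or 0.22 to 0.33 (mostly early). This is fair, and it marks the lower part of the plausible range.
- *Early terminators are to be assessed.* Where such a count is usable the bias falls, for example from 0.60 to 0.40, but it does not vanish.
- *The distorted baseline slope* (1.04 to 0.91 under random, mostly early dropout) is a nuisance parameter that no endpoint reports. This is correct.
- *The mapping is inferred and the code is schematic.* Section 7.1 leaves detail to the SAP, which was not available here. The mapping is indeed inferred, but the protocol prints this list, and no numbering makes it complete.

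**Conclusion.** The concern holds. As printed, the statement omits the baseline count (the likelier reading) or the Week 12 count (the other reading), and it does not match the IGA statement beside it.

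Taking Baseline as the omission, a realistic figure for the inflammatory contrast is roughly 0.2 to 0.7 lesion, if baseline-related dropout occurs in the active arm only and is evenly spread or mostly early. It is about nil when the dependence is absent, equal across arms, or acts through observed post-baseline counts. Shifts of a lesion or more need extreme patterns and should carry little weight. All these sizes rest on assumed SDs, correlations, effects and dropout rates.

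The point would not change the main result. It should still be fixed, because the prespecified code is incomplete and the repair removes the bias in every scenario examined.

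**What to change.** Include the baseline lesion count in the imputation list and define the index against the visit schedule. For example, use `var lescnt1-lescnt5;` with `lescnt1` = Baseline, `lescnt2` = Week 2, `lescnt3` = Week 4, `lescnt4` = Week 8 and `lescnt5` = Week 12. Any other naming serves if it is defined and covers all five time points.

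The cost is one token of code and one line of definition. Baseline counts are collected for everyone, so no new data are needed. At 50 v 25 + 25 the five-variable model still runs by arm, and the pooled SE is slightly smaller (2.45 against 2.53 under random dropout).
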